7.6.2 Secondary endpoints

- % change in surgical approach for all patients comprising:
 - % with less invasive approach
 - % with no change in surgical approach
 - % with more invasive approach
- % change in VTT length across all timepoints for each patient (see [Section 6](#))
- % change in VTT length, stratified by pre-surgical RECIST response (as provided by site)
- Waterfall plot of % change in VTT length, coloured by pre-surgical RECIST response (as provide by site)
- Radiological response (RECIST) data (pre-surgical timepoints only), comprising:
 - % with complete response
 - % with partial response
 - % with stable disease
 - % with progressive disease
 - comparison with RECIST values calculated in-house where possible
- Evaluation of morbidity assessed by Clavian-Dindo classification
 - % with grade I to V complications

7.7 Additional analyses

The correlation of the drug exposure with the response of the VTT will be examined by presenting the Pearson's correlation coefficient between the total dose of drug received and the percent reduction in VTT.

8 Statistical Methods for the Analysis of the Study Data

As this is a single arm feasibility study results will be presented as counts, frequencies and percentages. 80% confidence intervals will be provided for the percentage of evaluable patients with an improvement in their Mayo Classification between screening and week 9, percentage change in surgical approach and percentage change in VTT height.

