## 3. TRIAL DESIGN

### 3.1. General Design

NAXIVA is a single arm, single agent, open label, phase II feasibility study of axitinib in patients with both metastatic and non-metastatic renal cell carcinoma of clear cell histology. 20 patients will be recruited from multiple centres within the United Kingdom.

Patients who have signed informed consent and who have met all eligibility criteria will be registered into the trial.

The starting dose of axitinib will be 5mg BID and escalated to 7mg BID and then 10mg BID. A dose modification assessment will take place every 2 weeks in clinic during the 8 week pre-surgical treatment period and will be dependent on tolerability of treatment. Patients will follow an aggressive axitinib dose escalation process within the 8 week period to a maximum of 10mg BID. Patients should stop axitinib a minimum of 36 hours and a maximum of 7 days prior to surgery in week 9.

Blood, urine and tissue samples will be taken prior to and during therapy to evaluate biomarkers of treatment response. Nephrectomy and IVC tumour thrombectomy will be planned for all patients on the trial.

Response to axitinib in VTT, primary tumour and any RECIST measureable lesion will be correlated with changes in molecular markers.

Patients will be followed up in clinic at 6 & 12 weeks post surgery.

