### **Primary Safety Endpoints**

Thirteen patients will be recruited at first; if at least 1 patient has an improvement in the Mayo classification a further 7 patients would be recruited (to the final total of 20 patients who have received study drug), to receive study drug. At least 3 patients showing reductions in Mayo score are required for a positive trial. The early stopping rules are:

- (1) If a single M0 patient progresses to the point where surgery is no longer possible, then recruitment of new patients will be suspended following a review by the data monitoring committee (DMC).
- (2) If a single M0 patient becomes M1 recruitment of new patients will be suspended following a review by the DMC.
- (3) If in 3 patients the VTT extends but patients remain surgically resectable the trial will close. If the VTT has extended the patient will be expedited and operated on as soon as possible.

Where there is diagnostic doubt at site, the week 3 MRI abdomen scans (and CT chest for M0 patients) a central review will be conducted to determine if a patient has progressed as per RECIST 1.1 criteria. In addition those particular patient cases will be discussed on an individual basis by the trial steering committee (TSC).

The central review for final analysis will be conducted by radiologists based at Addenbrooke's Hospital.

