## **4. TREATMENT**

### **4.1. Treatment Schedule**

Patients should start axitinib treatment on day 1, week 1 of the study and continue for 8 weeks.

Patients will be prescribed 1 pack (28 tablets) of 5mg BID at week 1. Patients will then be prescribed further axitinib every 2 weeks following the dose modification schedule detailed in

section 4.2 (depending on toxicities and blood pressure). Doses should be taken appropriately 12 hours apart and patients should be instructed to take their doses at approximately the same time each day with or without food as per instruction. On clinic days only, patients will be advised to fast for 6 hours prior to their clinic visit.

Patients should be advised to stop axitinib treatment a minimum of 36 hours and maximum of 7 days prior to week 9 surgery and tissue collection.

If a patient vomits or misses a dose, an additional dose should not be taken. The next prescribed dose should be taken at the usual time. If the patient reports having missed a dose or vomiting, this should be recorded in the source documents and case report forms (CRFs).

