#### **4.3. Duration of Treatment**

Treatment with study drug should be discontinued if it is considered to be in the best interest of the patient. Reasons for treatment discontinuation include:

- Disease progression
- Occurrence of intolerable side effects
- Pregnancy
- Patient withdrawal of consent or non-compliance

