#### **5.2.4. Assessment at day 1, week 3 (within 7 days)**

- Laboratory determinations
  - FBC, coagulation, glucose, renal and liver function, serum calcium, CRP and LDH
  - Urinalysis
  - Serum thyroid function tests (Free T4 and TSH)
  - Blood and urine sample for biomarker analysis (NB. patients should be asked to fast for 6 hours prior to urine analysis)
- Clinical assessment
  - ECOG & Karnofsky performance status (appendix 1)
  - Body weight
  - Height
  - Blood pressure
  - Heart rate
  - Respiratory rate
  - Temperature
  - Symptom assessment (CTCAE V4)
  - Assessment for concomitant medications
  - Assessment of compliance with study medication
  - Dose evaluation and escalation (where appropriate)
- Radiological assessment
  - CT chest for IVC VTT (M0 patients only) to check for development of metastasis
  - Diffusion/ contrast enhanced MRI abdomen (all patients)
- Pharmacy
  - Dispense axitinib (dose modification as per section 4.2 if applicable)

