5.2 Early stopping rules

Patient safety will be ensured by applying the following early stopping rules:

- (1) If a single M0 (staging data: cancer has not spread to other parts of the body) patient progresses to the point where surgery is no longer possible, then recruitment of new patients will be suspended following a review by the data monitoring committee (DMC)
- (2) If a single M0 (staging data: cancer has not spread to other parts of the body) patient becomes a M1 (staging data: cancer has spread to other parts of the body) patient, recruitment of new patients will be suspended following a review by the DMC.
- (3) If in 3 patients the VTT extends (as indicated by an increase in Mayo classification) but patients remain surgically resectable the trial will close. If the VTT has extended the patient will be expedited and operated on as soon as possible.

6 Efficacy evaluations

Note that these evaluations will be made for both the evaluable and ITT populations. This represents a sensitivity analysis that assesses whether results are robust in the ITT population.

This study will use the following efficacy parameters:

- At least 3 evaluable patients showing improvement in disease extent between screening and week 9 are required for a positive trial.
- The change in Mayo classification between screening and week 9 in evaluable patients will be presented with the percentage of patients with an improvement, no change and a deterioration in Mayo classification shown. Percentages will be calculated using both the evaluable population and the ITT population.
- The VTT length measurement will be calculated as the sum of: (1) length of IVC tumour thrombus ABOVE renal vein (measured from ostium of RV+IVC to tip of tumour thrombus); (2) length of IVC tumour thrombus BELOW renal vein (measured from ostium of RV+IVC to tip of tumour thrombus) and (3) length of RV thrombus. Those patients who are identified as “main renal vein” will only have the third value populated. Any values that are missing cannot be assumed to represent 0 and must be clarified either via contact with sites or by manual checking of the paper CRF.

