7.4 Delivery of study therapy (evaluable population)

- Total dose (mg) taken per patient separately for axitinib (median, IQ range and range)
- Total dose (mg) missed per patient separately for axitinib (median, IQ range and range)
- Percentage of intended dose taken per patient (taken/(taken+missed)) separately for axitinib (median, IQ range and range)
- Reasons for missed doses will be tabulated; further specification of “other” reasons will be listed.
- The number of dose reductions per patient
- The number of dose escalations per patient
- Reasons why axitinib was reduced to 3mg BID
- Reasons why axitinib was reduced to 2mg BID
- Reasons for stopping trial drug will be tabulated; “other” reasons and “Adverse event/toxicity” reasons will be listed

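### SAP 7.7 correlates total dose with thrombus shrinkage, but growth seen early ends dosing, so early stoppers pull the coefficient upward even if dose has no effect

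*SAP*

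**What the plan says.** SAP 7.7 sets out to examine how drug exposure relates to thrombus response, using the Pearson "correlation coefficient between the total dose of drug received and the percent reduction in VTT". It states no adjustment, common exposure window, restriction or caveat. It does not say which scan supplies the percent reduction for a patient who stops early. SAP 7.4 reports the matching dose variable, "Total dose (mg) taken per patient separately for axitinib (median, IQ range and range".

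Four other provisions determine how total dose arises:

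- Protocol 4.1: "Patients should start axitinib treatment on day 1, week 1 of the study and continue for 8 weeks".
- Protocol 3.1: "The starting dose of axitinib will be 5mg BID and escalated to 7mg BID and then 10mg BID", with dose assessed every 2 weeks.
- Protocol 5.2.4, week 3: "Diffusion/ contrast enhanced MRI abdomen (all patients". This is the only scheduled abdominal MRI between baseline and week 9.
- Protocol 3.4, Primary Safety Endpoints: "If the VTT has extended the patient will be expedited and operated on as soon as possible". SAP 5.2 repeats the rule and defines extension for the closure count: "If in 3 patients the VTT extends (as indicated by an increase in Mayo classification) but patients remain surgically resectable the trial will close". Protocol 4.3 also lists "Disease progression" among the reasons for discontinuing drug.

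**The concern.** Total dose is daily dose summed over days on drug. When thrombus growth cuts the number of days, the outcome determines the exposure. A patient who grows early has both a low total and a negative percent reduction, which places a point in the lower left of the scatter. In 20 patients, one or two such points can produce a visible positive slope although dose does nothing.

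This is the only exposure-response analysis in the SAP. A reader would naturally take a positive coefficient to mean that more drug shrinks thrombus more, when it could reflect only the rule for handling growth.

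**Working it through.** **The plan's own figures.** The documents give no figure for the correlation. The related figures reproduce. The two-stage design (13 then 20 patients, success at 3 or more) has one-sided alpha 0.0736 at 5% and power 0.903 at 25%. The chance of 3 or more progressions in 20 at a 5% rate is 0.0755, against the stated bound of 7.5%, a rounding-level difference.

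**Step 1: total dose by path** (protocol dose levels, two doses a day, 14-day steps).

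- Full escalation: 2 × (5×14 + 7×14 + 10×28) = 896 mg.
- Starting dose throughout: 2 × 5 × 56 = 560 mg.
- Lowest reduction path in the dose table: 2 × (5×14 + 3×14 + 2×28) = 336 mg.
- Dosing ends at the week 3 visit: 2 × 5 × 14 = 140 mg.

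The early stopper therefore has 140/896 = 16% to 140/560 = 25% of the total of an 8-week patient at the starting dose or above, and 140/336 = 42% of the lowest 8-week path.

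**Step 2: how often this could happen.** At the 5% progression rate in protocol 9.2, 20 × 0.05 = 1 progression is expected, and the chance of at least one is 1 − 0.95^20 = 64%. At 10% it is 1 − 0.90^20 = 88%. These count any progression, so they are upper bounds for growth seen by week 3.

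**Step 3: effect on the coefficient.** Simulated trials of 20 patients with a true dose effect of zero. Assumptions, none given in the documents:

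- Percent reduction is normal with mean/SD 15/20 or 25/25.
- Dose paths are 40% full escalation, 20% to the middle step, 20% at the starting dose and 20% reduced, all independent of response.
- The k patients with the worst thrombus change stop early and stay in the calculation.

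| Early stops for growth (k) | Mean r, dosing ends day 14 | Mean r, dosing ends day 21 |
|---|---|---|
| 0 | 0.00 | 0.00 |
| 1 | 0.25 | 0.23 |
| 2 | 0.39–0.40 | 0.36 |
| 3 | 0.49 | 0.45 |

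Across somewhat later stopping times and the assumed settings, a fair summary is about 0.2, 0.33–0.36 and 0.42–0.46 for one, two and three stops. If three patients chosen at random stop at week 3, mean r is about 0.00. The shift therefore comes from the link between growth and stopping, not from short treatment as such.

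**Step 4: other exposure measures, same data (day 14 stops).** Mean daily dose while on drug leaves r of 0.07–0.08, 0.13–0.14 and 0.18 for one, two and three stops, because escalation itself takes time. Percentage of scheduled dose taken while on drug gives about 0.00. The definition of "missed" matters, however. If doses after the stop counted as missed, a week 3 stopper at the starting dose would score 140/(140 + 420) = 25%, and the problem would return.

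**The case against.** A reader might infer that the analysis is bound to show a false positive dose-response. The documents do not support that, for these reasons:

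- **No early growth, no bias by this route.** Growth first seen at week 9 costs no dose. At a 5% rate, 0.95^20 = 36% of 20-patient trials have no progression at all, and the protocol's background reports 0 of 12 sunitinib patients with an increase in level.
- **Small growth need not end dosing.** SAP 5.2 ties extension to a rise in Mayo class, and no rule expedites a patient for a slight increase in length. With an assumed correlation of 0.6 between week 3 and week 9 change, stopping only for week 3 growth above 20% gives mean r of 0.02 to 0.09. Above 10%, it gives 0.14 to 0.30.
- **High growth rates mostly cannot reach 20 patients.** At 23%, the chance of 3 or more extensions in 20 is 0.87, and the trial closes at 3 resectable ones. Larger coefficients from such scenarios should not be cited.
- **Toxicity can push the other way.** If systemic exposure drives both shrinkage and dose reduction (assumed exposure-shrinkage correlation 0.3 to 0.5), r with no early stops is −0.18 to −0.31. With one stop it is 0.12 to 0.03, and with three 0.41 to 0.35.
- **Early stoppers may not enter.** The week 3 substitution in SAP 7.6.1 is stated for primary endpoint assessments only. If SAP 7.7 uses week 9 change, patients without that scan drop out unless imputed.
- **No test is planned.** SAP 7.7 only presents a coefficient, so significance rates describe nothing in the plan. No passage links it to phase 3 dosing.

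All of this stands as a limit on certainty and size. It does not remove the mechanism. The listings of stop reasons and extensions, and the waterfall plot of length change, help a careful reader but do not correct the coefficient.

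**Conclusion.** The concern holds conditionally. If patients stopped early for growth enter the SAP 7.7 coefficient, that route pulls it upward with no dose effect: by about 0.2 for one patient, 0.33–0.36 for two and 0.42–0.46 for three. With none there is no pull.

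These sizes rest on assumed response means, SDs and dose mix, on the stoppers being the patients with the worst change, and on dose being otherwise unrelated to response. The direction of this component is fixed by the protocol's handling of growth. The sign of the observed coefficient is not.

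This is a small point on an additional analysis. It does not touch the primary endpoint, the futility look or the success criterion.

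**What to change.** In SAP 7.7:

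- Replace total dose with an exposure measure that time on drug does not drive. One option is the percentage of scheduled dose taken while on drug. SAP 7.4 already plans a taken/(taken + missed) figure, but it must state that doses after a stop for progression are not counted as missed. The other option is dose up to the week 3 scan.
- Name the scan that supplies the percent reduction, and count dose only up to that scan.
- Plot all patients, marking early stoppers and their stop reason.
- Show the coefficient among patients treated for the full 8 weeks only as a sensitivity result. That group is selected partly on response and loses those who stopped for toxicity. With an assumed toxicity-response link of 0.4, its coefficient was −0.28 to −0.33.
- Report any all-patient total-dose coefficient as descriptive, not as evidence of exposure-response.

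The cost is a few lines of SAP text, slightly more analysis and one plot, with no new data and no change to patient management. The downside is less spread in the exposure measure. Since all patients start at the same dose, dose to week 3 in particular varies little beyond missed doses and interruptions.

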1.1 Primary endpoint

The primary end-point for this study is the percentage of evaluable patients with an improvement in disease as a result of taking the study drug. The definition of an improvement will vary according to the patient's Mayo Level as captured at screening:

- **For patients presenting at screening with a Mayo Classification of Level 1 or above**, an improvement in disease will be represented by a reduction in their Mayo Classification at week 9.
- **For patients presenting at screening with a Mayo Classification of Level 0**, an improvement in disease will be represented by either:
 - a change of tumor thrombus from main renal vein to branches of the renal vein (on the right);
or
 - a change of tumor thrombus from main renal vein to the renal vein lateral to the gonadal vein (on the left).

See [Section 6.1](#) for further details regarding the definition of improvement in relation to the Mayo classification and the surgical approach classification.

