6.1 Additional definitions

Definitions of the Mayo classification and surgical approach classification systems that should be used to define improvement are shown below:

Mayo classification (levels are ordered by increasing extensiveness):

- Level 0: thrombus limited to the renal vein
- Level 1: into IVC <2cm from renal vein ostium level
- Level 2: IVC extension >2cm from renal vein ostium and below hepatic vein
- Level 3: thrombus at the level of or above the hepatic veins but below the diaphragm
- Level 4: thrombus extending above the diaphragm.

Tumour thrombus surgical management approach classification (approaches are ordered by increasing invasiveness):

1. Thrombus - Milked back into renal vein and side clamped
2. Infra-hepatic (IVC clamping with no liver mobilisation)
3. Retro-hepatic (liver mobilisation and clamping below hepatic veins)
4. Retro-hepatic (liver mobilisation and clamping above hepatic veins)
5. Supra-hepatic (infradiaphragmatic)

6. Supra-hepatic (supradiaphragmatic)

Note that efficacy outcomes can be expressed as a percentage of the ITT population or the evaluable population (meaning that the denominator should change to be either the size of the relevant population).

7 Tabulations, Figures and Listings

This section is the complete operational specification for the statistical analysis and subsequent presentation of that analysis for the lifetime of this trial. Throughout this section, tabulations consist of counts and percentages per category unless stated otherwise. Listings will include the patient identifier and the specific data for that listing.

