7.6.1 Primary endpoints

NB. For all primary endpoint assessments, if a patient does not have a week 9 scan, then their week 3 scan (if available) should be used instead.

7.6.1.1 For patients presenting at screening with a Mayo Classification of Level 1 or above

- The number and percentage of patients with an improvement in the Mayo Classification between screening and week 9 (see [Section 6.1](#) for Mayo classification system).
- The number and percentage of patients with no change in the Mayo Classification between screening and week 9 (see [Section 6.1](#) for Mayo classification system).
- The number and percentage of patients with deterioration in the Mayo Classification between screening and week 9 (see [Section 6.1](#) for Mayo classification system).

7.6.1.2 For patients presenting at screening with a Mayo Classification of Level 0

- The number and percentage of patients demonstrating improvement in status, i.e.:

- For patients presenting with right renal vein tumour thrombus: a change of tumour thrombus from main renal vein to branches of the renal vein between screening and week 9.
- For patients presenting with left renal vein tumour thrombus: a change of tumour thrombus from the main renal vein between screening and week 9 as follows:
 - If the patient is lateral to the gonadal vein at screening, a change from the main renal vein into the segmental veins
 - If the patient is medial to the gonadal vein at screening, a change from the main renal vein medial to the gonadal vein to the renal vein lateral to the gonadal vein
- The number and percentage of patients with no change in tumour thrombus status (i.e., tumour still present in the main renal vein and medial to the gonadal vein (on left side)) between screening and week 9.
- The number and percentage of patients demonstrating an extension of the thrombus into the inferior vena cava between screening and week 9.

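### SAP 8 names its primary 80% interval for Mayo improvement, while SAP 1.1 and the SAP 3.1.2 and 6 decision rules use improvement in disease, which also counts Level 0 regression

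*SAP*

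**What the plan says.** - **SAP 1.1.** "The primary end-point for this study is the percentage of evaluable patients with an improvement in disease". The meaning of improvement depends on the screening level: a lower Mayo level at week 9 for Level 1 or above, and a defined regression within the renal vein, by side, for Level 0.
- **SAP 3.1.2.** The futility stop applies if no evaluable patient has improved in disease.
- **SAP 6.** The first bullet requires at least 3 evaluable patients with improvement in disease extent. The second presents change in Mayo classification, "with the percentage of patients with an improvement, no change and a deterioration in Mayo classification shown".
- **SAP 7.6.1.** Results are listed under 7.6.1.1 for Level 1 or above and under 7.6.1.2 for Level 0. No combined row follows. SAP 7 describes itself thus: "This section is the complete operational specification for the statistical analysis and subsequent presentation of that analysis".
- **SAP 8.** "80% confidence intervals will be provided for the percentage of evaluable patients with an improvement in their Mayo Classification between screening and week 9".
- **SAP 3.2.** 80% two-sided intervals by a two-stage method (Koyama and Chen) are planned for the proportions that go with the efficacy endpoints. None is named.
- **SAP 3.1 and 4.1.** The stage 1 rule is worded as improvement in Mayo classification. SAP 4.1 then words success as improvement in either disease or treatment.

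Patients with thrombus confined to the main renal vein are eligible (Protocol 3.2, criterion 5), and Protocol 1.5 explains why they are included.

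**The concern.** On the scale in SAP 6.1 no level lies below 0. An analyst who follows SAP 8 to the letter therefore counts every Level 0 patient in the denominator and none in the numerator, although SAP 1.1 gives those patients their own route to improvement. Whenever a Level 0 patient improves, the SAP 8 percentage is lower than the one SAP 1.1 defines.

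What is at stake is the headline estimate and its interval, not the count of at least 3. The one-sided 10% test and the 80% interval are meant to correspond (SAP 3.2). That holds only if both use the same numerator. Otherwise a trial declared positive could publish an interval that includes the 5% rate it has just rejected.

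**Working it through.** **Inputs.** Stage 1 of 13 patients, total 20, continue with at least 1 improver, positive with at least 3, rates 5% and 25% (SAP 4.1); 80% two-sided interval (SAP 3.2).

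**1. Reproduce the design.** P(positive) = Σ over x1 ≥ 1 of P(X1 = x1) × P(X2 ≥ 3 − x1), with X1 ~ Bin(13, p) and X2 ~ Bin(7, p).

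At p = 5%: 0.3512 × 0.0444 + 0.1109 × 0.3017 + 0.0245 = 0.0736.

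At p = 25% the same sum gives 0.903. So alpha is 7.36% and power 90.3%, in line with the plan's 10% and 90%.

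**2. Two-stage 80% intervals.** For t improvers after continuing to 20, the lower limit solves P(X1 ≥ 1, X ≥ t) = 0.10 and the upper limit solves P(X1 ≥ 1, X ≥ t + 1) = 0.90.

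| t of 20 | Estimate | 80% interval | One-sided p at 5% |
|---|---|---|---|
| 2 | 10% | 2.9% to 24.8% | 0.241 |
| 3 | 15% | 5.7% to 30.5% | 0.074 |

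Three improvers is the smallest count whose interval excludes 5%. This matches the success rule when both count the same thing.

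**3. One Level 0 improver is enough to separate them.** Take exactly 3 improvers of 20, one of them Level 0.
- By SAP 1.1: 3/20, interval 5.7% to 30.5%, excludes 5%, positive.
- By SAP 8 as worded: 2/20, interval 2.9% to 24.8%, includes 5%.
- By SAP 7.6.1, assuming for illustration 5 Level 0 patients: 2/15 = 13.3% and 1/5 = 20% with subgroup denominators, or 2/20 and 1/20 with the evaluable denominator. Only the second pair sums to 3/20.

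**4. How often this could happen.** The documents give neither the Level 0 share nor a Level 0 improvement rate, so both are assumed. Let the share be s, the rate at Level 1 or above 25%, and the rate at Level 0 q. Each patient is a Mayo improver with probability 0.25(1 − s) and a Level 0 improver with probability sq. Summing exactly over 13 + 7 patients, with continuation and success both on the pooled count, gives P(positive with fewer than 3 Mayo improvers) ÷ P(positive):

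| s | Expected Mayo-only rate | q = 25% | q = 5% |
|---|---|---|---|
| 10% | 22.5% | 0.0470/0.9030 = 5.2% | 0.0107/0.8648 = 1.2% |
| 20% | 20.0% | 0.1126/0.9030 = 12.5% | 0.0283/0.8153 = 3.5% |
| 30% | 17.5% | 0.1997/0.9030 = 22.1% | 0.0541/0.7529 = 7.2% |
| 40% | 15.0% | 0.3096/0.9030 = 34.3% | 0.0879/0.6765 = 13.0% |

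At q = 0 the proportion is zero.

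**The case against.** The strongest reply is that the SAP already holds what is needed. Four parts of it carry weight.

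- **SAP 3.2 may cover the pooled proportion.** Its two-stage intervals are for the efficacy-endpoint proportions, and the primary one in SAP 1.1 is pooled. This stands as a fair reading. A reader might infer that the deciding percentage gets no interval anywhere; the documents do not support that. What remains is that 3.2 names no proportion, and SAP 8, which does, names the Mayo one.
- **SAP 7.6.1 can yield the pooled figure.** Its two improvement numerators can be added. SAP 6.1 says that efficacy outcomes are expressed over the evaluable or ITT population, so the two percentages may share a denominator and sum to the pooled one. It would go too far to say the pooled result cannot be recovered. Still, no pooled percentage or interval is printed, and the row denominators are not stated.
- **SAP 8 may be carried-over wording.** It says thrombus height, as the protocol does, where the rest of the SAP says length, and Protocol 3.4 defines the endpoint by Mayo improvement alone. A slip is plausible. But SAP 1.1 and 7.6.1.2 treat Level 0 improvement as something other than a Mayo reduction, so the words in SAP 8 have a different literal meaning.
- **The Mayo bullet in SAP 6 is not a rival primary endpoint.** It is a distribution of change, placed after the success criterion. That stands.

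A reader might also infer that a two-stage interval cannot apply to a Mayo-only count, because the trial could enter stage 2 with no Mayo improver. That follows from SAP 3.1.2. SAP 3.1 and 4.1, read as literally, word the stage 1 rule on Mayo improvement. The argument depends on which section governs, which is itself a reason to reconcile them.

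**Conclusion.** The inconsistency is real and should be corrected before analysis. SAP 1.1, 3.1.2 and the SAP 6 success criterion use improvement in disease; SAP 8 attaches its named interval to improvement in Mayo classification; SAP 7.6.1 prints no pooled row; SAP 3.1 and 4.1 add further wordings.

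Its size depends on Level 0 patients. With no Level 0 improver there is no difference. With exactly 3 improvers, one of them Level 0, the estimate falls from 15% to 10% and the interval changes from excluding 5% to including it. For assumed Level 0 shares of 10% to 40%, with 25% improvement at Level 1 or above, about 5% to 34% of positive trials would show fewer than 3 Mayo improvers if Level 0 patients also improve at 25%, and about 1% to 13% if they improve at 5%. The upper values need a large share and a high Level 0 rate together, so they are bounds of an assumed range, not forecasts.

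A reader might conclude that the published primary estimate will certainly differ from the quantity that decides the trial. The documents do not go that far, since SAP 3.2 and 6.1 leave room for the right figure. They show that the plan does not fix which percentage is the headline.

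**What to change.** 1. In SAP 8, replace improvement in Mayo Classification with improvement as defined in SAP 1.1. In SAP 3.2, name that pooled proportion as the one that receives the two-stage 80% interval.
2. In SAP 7.6.1, add one row: number improved by either route over all evaluable patients, with the ITT version as sensitivity analysis. SAP 7.6.1.2 has a left-sided route (lateral to the gonadal vein at screening, then into the segmental veins) that SAP 1.1 lacks, so the definition should be made the same in both places.
3. State the denominators of the Level 1 or above and Level 0 rows. Keep those rows and the Mayo-only change as descriptive, without the two-stage interval.
4. Reconcile SAP 3.1, 3.1.2, 4.1 and 6 so that the futility rule, the success rule and the reported estimate all use the SAP 1.1 definition.

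The cost is SAP wording and one table row. No new data are needed, and the 13 + 7 design figures stay as they are. The small downside is that the subgroup and Mayo-only rows become descriptive.
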